12.0 CRITERIA FOR THERAPEUTIC RESPONSE/OUTCOME ASSESSMENT

12.1 Antitumor Effect – Solid Tumors

During the treatment period, patients will be evaluated prior to treatment and re-evaluated for response every 8 weeks for four scans. Patients will then be imaged approximately every 12 weeks until disease progression is noted. If a patient has a durable response of > 2 year, patients can be imaged every 6 months. Response and progression will be evaluated in this study using the new international criteria proposed by the revised Response Evaluation Criteria in Solid Tumors (RECIST) guideline (version 1.1) [32]. Changes in the largest diameter (unidimensional measurement) of the tumor lesions and the shortest diameter in the case of malignant lymph nodes are used in the RECIST. Choi response criteria as outlined in GIST will be used as a secondary response [33]. In addition, patients will be evaluated by FDG-PET prior to treatment and re-evaluated for response 3 weeks after the combination treatment based on the EORTC criteria[34]. This will also be used as secondary response.

12.1.1 Definitions

Evaluable for toxicity. All Phase Ib patients will be evaluable for toxicity from the time of their first treatment with imatinib plus BGJ398. All Phase II patients will be evaluable for toxicity from the time of their first treatment with imatinib alone.

Evaluable for efficacy. Only those patients who have measurable disease present at baseline and have received at least one dose of imatinib plus BGJ398 therapy will be considered evaluable for efficacy. These patients will have their response classified according to the definitions stated below. Patients on the Phase II portion who are taken off study prior to receiving their first dose of BGJ398 for reasons other than progressive disease are considered replaceable for the purposes of evaluating primary and secondary endpoints.

Evaluable Non-Target Disease Response. Patients who have lesions present at baseline that are evaluable but do not meet the definitions of measurable disease, have received at least one cycle of therapy, and have had their disease re-evaluated will be considered evaluable for non-target disease. The response assessment is based on the presence, absence, or unequivocal progression of the lesions.

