The mechanisms of imatinib resistance in GIST are complex and heterogeneous. Approximately 5% of patients have primary resistance to imatinib with progression of disease within two months of treatment. About 14% of patients develop early resistance to imatinib after approximately 4 months

of treatment. The majority of patients develop resistance to imatinib after approximately 2-3 years of treatment [12]. Secondary mutations are rare in primary resistance, but are found in about 50-67% of patients with secondary resistance [16, 17]. The rest of secondary resistance has unknown etiologies. Other causes of secondary resistance are still being defined; researchers at MSKCC recently correlated an intratumoral immune response with imatinib resistance in GIST [18]. Moreover, recent data suggest that the GIST stem/progenitors are *KIT*-low and *KIT*-independent and therefore imatinib-insensitive [19], which might account for part of the resistance mechanisms in both primary and secondary resistance settings. In addition, activation of alternative signaling pathways such as the MAP Kinase pathway and the PI3K pathway have also been correlated with the development of primary imatinib resistance [20]. In summary, although *KIT* inhibitors have revolutionized the treatment of advanced GIST, the efficacy is not indefinite and it is not curative in most advanced GIST patients [3, 4, 12, 21-24].

[figure not shown]
[figure not shown]
[figure not shown]
Here, we propose a novel strategy that combines inhibition of both *KIT* and FGF signaling pathways. The goal of such dual inhibition is to not only target *KIT*, but also the MAP Kinase pathway (via FGF signaling). We have recently discovered that the MAP Kinase pathway plays a major role in the pathogenesis and propagation of GIST

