The secondary endpoints of the phase 1b portion are (1) Response Rate (RR) defined by RECIST 1.1 criteria and by CHOI criteria, (2) Progression Free Survival (PFS), (3) Clinical Benefit Rate (CBR) at 32 weeks, and (4) BGJ398 pharmacokinetic parameters, such as area under the curve (AUC) and maximum concentration (C_{max}). RR will be estimated as the proportion of patients who have complete response or partial response for each criterion. PFS will be calculated using Kaplan-Meier estimate among all patients enrolled at each dose level. Patients who have not experienced the event of interest by the end of the study will be censored at the time of the last follow-up. Plasma concentrations of BGJ398 will be analyzed at multiple time points and expressed as a mean +/- SE.

The phase 1b portion of the study will have a minimum sample size of 6 patients and a maximum of 30. We expect to accrue approximately 2 patients each month, and hence expect to finish the phase 1b portion of the study in approximately 9-15 months.

Evaluable patients for safety analysis include all patients who have received one dose of imatinib plus BGJ398. Patients who stop therapy before Cycle 2, Day 1 for reasons other than toxicity will be replaced in the Phase I study for the purposes of evaluating the DLT. Evaluable patients for efficacy include all patients who have received one dose of imatinib plus BGJ398. Patients who are missing an assessment of response post baseline will be considered non-responders for that time point.

Patients on the Phase I portion of the study will not be included in the final efficacy analysis due to differences in the eligibility criteria in the two phases.

Phase 2 Portion Study Design and Endpoint Assessment

The primary endpoint of the phase II portion of the study is to assess Response Rate (CR+PR, RECIST 1.1) after 32 weeks of combination therapy. In order to detect a 20% improvement in the RR over imatinib alone (unacceptable rate of 45%; acceptable rate of 65%), 44 Phase II patients will be enrolled. At the end of the study, if > 24 patients have had a documented response by RECIST 1.1, the study will be considered positive and the treatment regimen will be considered worthy of further investigation. The study design is based on an exact Binomial test and has a one-sided type I error of 0.08 and a type II error of 0.1.

We expect to accrue 2 patients each month, and hence expect to finish the phase 2 portion of the study in 24 months.

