Response rate (RECIST 1.1) will be determined as the proportion of patients evaluable for efficacy (defined as patients who receive at least one dose of the combination regimen) who have complete response or partial response defined by the RECIST 1.1 with a one-sided 90% confidence interval (CI) provided. Patients missing post baseline assessment of response will be considered non-responders for the primary endpoint at that time point.

The steady state serum imatinib trough levels will be obtained and evaluated in the two-week imatinib lead in phase (two samples/patient) and in the combination therapy phase (2 samples/patient) from all patients in the Phase II portion of the trial. We will evaluate the effects of BGJ398 on imatinib steady state trough levels by comparing the values at these two time points (before and after lead in period). We will compare the ranges we obtain with the ranges reported by Demetri et al JCO 2009 and assess whether the effects are considered subtherapeutic, therapeutic, or

MEMORIAL SLOAN-KETTERING CANCER CENTER
IRB PROTOCOL

IRB#: 14-140 A (7)

supra-therapeutic. This analysis may inform future trials with this combination and will not change the dose that will be given in the combination regimen.

The secondary endpoints of the phase 2 portion include:

- (1) RR by CHOI criteria. It will be determined as the proportion of patients evaluable for efficacy who have complete response or partial response defined by the CHOI criteria with a two-sided 95% CI provided.
- (2) RR by EORTC criteria. It will be determined as the proportion of patients evaluable for efficacy who have complete response or partial response defined by the EORTC criteria with a two-sided 95% CI provided.
- (3) Progression free survival and Overall Survival. PFS and OS will be calculated using a Kaplan-Meier estimate among all patients enrolled. They are defined from the start of imatinib treatment, i.e. the lead in period is included in this endpoint. Patients on the Phase II portion who stop study prior to receiving a dose of BGJ398 for reasons unrelated to progression (e.g. intolerance to imatinib) will be censored at the time of withdrawal. Patients who have not had the event of interest by the end of the study will be censored at the time of last follow-up.
- (4) Resectability rate. It will be calculated by the proportion of Phase II patients who have completed 1 cycle of treatment who have resection of their disease with a two-sided 95% CI provided.

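### A Phase II patient who progresses during the imatinib lead-in is neither replaced nor counted in the response rate, so the reported rate and its bound would be slightly too high

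*Combined protocol and SAP*

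**What the plan says.** **Lead-in.** Section 9.0 gives every Phase II patient two weeks of imatinib alone. BGJ398 is then added, and Cycle 1 Day 1 is the first day of the combination.

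**Denominator.** Section 12.1.1 says that only patients who have measurable disease and "have received at least one dose of imatinib plus BGJ398 therapy will be considered evaluable for efficacy". Section 14.0 computes the primary response rate on the same set, "defined as patients who receive at least one dose of the combination regimen", and attaches a one-sided 90% confidence interval.

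**Replacement.** Section 12.1.1 says that Phase II patients who leave before BGJ398 "for reasons other than progressive disease are considered replaceable for the purposes of evaluating primary and secondary endpoints". Section 13.0 repeats the exception for progressive disease and refers to Section 14 for inclusion in the analyses.

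**Design and rule.** Section 14.0 states that "44 Phase II patients will be enrolled". The trial is positive "if > 24 patients have had a documented response by RECIST 1.1". The design tests 45% against 65% and "has a one-sided type I error of 0.08 and a type II error of 0.1".

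**Other endpoints.** Section 14.0 estimates PFS among all enrolled patients from the start of imatinib. It censors only lead-in exits that are unrelated to progression.

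**The concern.** Refusing to replace a patient who progresses in the lead-in makes sense if that patient keeps a place among the 44 as a failure. The denominator rule does the opposite: without a combination dose, the patient is outside the response rate.

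No other sentence brings such a patient back. Section 13.0 defers to Section 14.0, which repeats the combination-dose requirement. The Section 14.0 rule that a missing assessment counts as non-response does not add undosed patients to the denominator. Section 14.0 does say how lead-in exits are handled for PFS, but has no counterpart for the primary endpoint.

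The same patient would therefore be a failure for PFS and absent from the response rate. At stake are the reported rate and its bound, and whether they describe the same patients as the more-than-24 rule.

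**Working it through.** **1. The plan's own figures.** Inputs from Section 14.0: n = 44, null 45%, alternative 65%, positive if more than 24 respond, that is X ≥ 25. With X binomial:
- P(X ≥ 25 | 44, 0.45) = 0.0775, which is the stated 0.08.
- P(X ≥ 25 | 44, 0.65) = 0.901, so the type II error is 0.099, the stated 0.1.
- A cut-off of 24 gives 0.131 and 0.944; a cut-off of 26 gives 0.042 and 0.837. Only 25 fits.

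**2. Effect on the reported result.** Let k patients progress in the lead-in, with exits for other reasons replaced. The denominator as written is n = 44 − k. The plan does not name the interval method; I assume the exact (Clopper-Pearson) bound, L = Beta⁻¹(0.10; x, n − x + 1).

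| k | n | 25/n | bound | 24/n | bound |
|---|---|---|---|---|---|
| 0 | 44 | 56.8% | 46.0% | 54.5% | 43.8% |
| 1 | 43 | 58.1% | 47.2% | 55.8% | 44.9% |
| 2 | 42 | 59.5% | 48.5% | 57.1% | 46.1% |

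With 44 patients, the bound and the count rule agree: 25 responders clear 45% and 24 do not. They still agree with 43. With 42, 24 responders give a bound above 45% while the rule says negative.

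**3. Effect on the decision.** A patient who leaves with progression before BGJ398 is not a responder under either denominator. The responder count, and so the decision, is the same whether or not the patient is counted.
- If 45% and 65% apply to treated patients, P(X ≥ 25) is 0.058 and 0.864 with 43 treated, and 0.042 and 0.818 with 42. Adding one or two certain non-responders to the denominator changes none of these.
- If the rates apply to all 44, the rates among 43 treated are 0.45 × 44/43 = 0.460 and 0.65 × 44/43 = 0.665, giving 0.075 and 0.906. With 42 treated the results are 0.073 and 0.911.

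The type I error does not exceed 0.0775 in any of these cases.

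**4. How many such patients.** The nearest figure, in Section 3.1.1, is: "Approximately 5% of patients have primary resistance to imatinib with progression of disease within two months of treatment". The documents give no two-week rate, so I take a range.
- Spread evenly over 8 weeks: 5% × 2/8 = 1.25%. Expected number 44 × 0.0125 = 0.55. P(0) = 0.9875⁴⁴ = 0.57; P(1) = 44 × 0.0125 × 0.9875⁴³ = 0.32; P(2 or more) = 0.105.
- All 5% in the lead-in, as an upper extreme: expected number 44 × 0.05 = 2.2. P(0) = 0.95⁴⁴ = 0.105; P(1) = 44 × 0.05 × 0.95⁴³ = 0.242; P(2 or more) = 0.653.

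**5. How often the bound and the rule would disagree at 24 responders.** Sum over k ≥ 2 of P(k lead-in progressors) × P(X = 24 | 44 − k, p), for p from 0.45 to 0.65. The result is about 0.4% to 1.3% under the even spread and about 2% to 8% under the upper extreme.

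**The case against.** **The event may never occur.** Under the even spread, no lead-in progressor is the likeliest outcome (57%). Table 11 schedules the first CT after two combination cycles, so no scan falls in the lead-in, and its footnote asks for radiologic documentation when a patient is removed for progression. Section 12.1.5 notes that GIST often enlarges early on KIT inhibition before it shrinks. All of this stands, and the point is conditional. Still, both replacement clauses expressly provide for progression before BGJ398, so the plan should say how such a patient is counted.

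**A treated-only denominator is defensible.** The endpoint is response to the combination, and early failures remain visible in PFS. If the target population is patients who received the combination, the rate is not biased for that target. But then withholding replacement for progression has no evident purpose, and the rate describes fewer patients than the 44 to which the rule and error rates refer. The upward bias is relative to those 44.

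**A reader might infer loss of power or false-positive inflation.** The documents support neither. Success is a count of responders, and step 3 shows that the denominator leaves it untouched. The figures 0.864 and 0.818 reflect fewer treated patients if 65% applies to treated patients; they are the same whether or not lead-in progressors are counted. Inflation would need the cut-off to be rescaled as a proportion above 24/44, giving a type I error of 0.102 with 43 patients and 0.132 with 42. The plan nowhere rescales it.

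**Conclusion.** The gap is real, conditional and small. As written, a patient who progresses in the lead-in is left out of the primary response rate and not replaced, while counting as a PFS event. The go/no-go decision and its type I error are unaffected.

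At 25 responders, the reported rate rises by 1.3 percentage points with one such patient (58.1 − 56.8) and by 2.7 with two (59.5 − 56.8); the one-sided bound rises from 46.0% to 47.2% or 48.5%. A conflict between bound and rule at 24 responders does not arise with one such patient; it needs at least two. Under the even spread this is rare.

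These conclusions rest on an exact interval, on replacement of lead-in exits for other reasons, and on an assumed 0 to 2 lead-in progressors. It would go too far to say that the evaluable number will fall below 44, or that the trial is underpowered because of the denominator.

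**What to change.** State in Sections 12.1.1 and 14.0 that a Phase II patient who progresses before the first BGJ398 dose stays in the primary response-rate denominator as a non-responder, and that only lead-in exits for other reasons are replaced. Section 13.0 says only that such patients may be replaced; that wording should be made firm, so that the analysis set is exactly 44. The reported rate, its bound and the more-than-24 rule then refer to the same patients.

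Replacing lead-in progressors instead would bring the number back to 44 but still leave known failures out of the rate.

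The cost is a sentence in each section and a reported rate that may be slightly lower. It needs no extra visits and no change to treatment. It should not be presented as restoring power.

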12.1.2 Disease Parameters

Measurable disease. Measurable lesions are defined as those that can be accurately measured in at least one dimension (longest diameter to be recorded for non-nodal lesions and short axis for nodal lesions) as >20 mm by chest x-ray, as >10 mm with CT scan or MRI, or >10 mm with calipers by clinical exam. All tumor measurements must be recorded in millimeters (or decimal fractions of centimeters).

Non-measurable disease. All other lesions (or sites of disease), including small lesions (longest diameter <10 mm or pathological lymph nodes with ≥ 10 to <15 mm short axis), are considered non-measurable disease. Bone lesions, leptomeningeal disease, ascites, pleural/pericardial effusions,

MEMORIAL SLOAN-KETTERING CANCER CENTER
IRB PROTOCOL

IRB#: 14-140 A (7)

lymphangitis cutis/pulmonitis, inflammatory breast disease, and abdominal masses (not followed by CT or MRI), are considered as non-measurable.

Target lesions. All measurable lesions up to a maximum of 2 lesions per organ and 5 lesions in total, representative of all involved organs, should be identified as target lesions and recorded and measured at baseline. Target lesions should be selected on the basis of their size (lesions with the longest diameter), be representative of all involved organs, but in addition should be those that lend themselves to reproducible repeated measurements. It may be the case that, on occasion, the largest lesion does not lend itself to reproducible measurement in which circumstance the next largest lesion which can be measured reproducibly should be selected. A sum of the diameters (longest for non-nodal lesions, short axis for nodal lesions) for all target lesions will be calculated and reported as the baseline sum diameters. If lymph nodes are to be included in the sum, then only the short axis is added into the sum. The baseline sum diameters will be used as reference to further characterize any objective tumor regression in the measurable dimension of the disease.

Non-target lesions. All other lesions (or sites of disease) including any measurable lesions over and above the 5 target lesions should be identified as non-target lesions and should also be recorded at baseline. Measurements of these lesions are not required, but the presence, absence, or in rare cases unequivocal progression of each should be noted throughout follow-up.

12.1.3 Methods for Evaluation of Measurable Disease

All measurements should be taken and recorded in metric notation using a ruler or calipers. All baseline evaluations should be performed as closely as possible to the beginning of treatment and never more than 4 weeks before the beginning of the treatment.

The same method of assessment and the same technique should be used to characterize each identified and reported lesion at baseline and during follow-up portion of study. Imaging-based evaluation is preferred to evaluation by clinical examination unless the lesion(s) being followed cannot be imaged but are assessable by clinical exam.

Clinical lesions. Clinical lesions will only be considered measurable when they are superficial (e.g., skin nodules and palpable lymph nodes) and ≥ 10 mm diameter as assessed using calipers (e.g., skin nodules). In the case of skin lesions, documentation by color photography, including a ruler to estimate the size of the lesion, is recommended.

Chest x-ray. Lesions on chest x-ray are acceptable as measurable lesions when they are clearly defined and surrounded by aerated lung. However, CT is preferable.

Conventional CT and MRI. This guideline has defined measurability of lesions on CT scan based on the assumption that CT slice thickness is 5 mm or less. If CT scans have slice thickness greater than 5 mm, the minimum size for a measurable lesion should be twice the slice thickness. MRI is also acceptable in certain situations (e.g. for body scans).

Use of MRI remains a complex issue. MRI has excellent contrast, spatial, and temporal resolution; however, there are many image acquisition variables involved in MRI, which greatly impact image quality, lesion conspicuity, and measurement. Furthermore, the availability of MRI is variable globally. As with CT, if an MRI is performed, the technical specifications of the scanning sequences

MEMORIAL SLOAN-KETTERING CANCER CENTER IRB PROTOCOL

IRB#: 14-140 A (7)

used should be optimized for the evaluation of the type and site of disease. Furthermore, as with CT, the modality used at follow-up should be the same as was used at baseline and the lesions should be measured/assessed on the same pulse sequence. It is beyond the scope of the RECIST guidelines to prescribe specific MRI pulse sequence parameters for all scanners, body parts, and diseases. Ideally, the same type of scanner should be used and the image acquisition protocol should be followed as closely as possible to prior scans. Body scans should be performed with breath-hold scanning techniques, if possible.

12.1.4 Primary Response Criteria (RECIST 1.1)

12.1.4.1 Evaluation of Target Lesions

Complete Response (CR): Disappearance of all target lesions. Any pathological lymph nodes (whether target or non-target) must have reduction in short axis to <10 mm.

Partial Response (PR): At least a 30% decrease in the sum of the diameters of target lesions, taking as reference the baseline sum diameters.

Progressive Disease (PD): At least a 20% increase in the sum of the diameters of target lesions, taking as reference the smallest sum on study (this includes the baseline sum if that is the smallest on study). In addition to the relative increase of 20%, the sum must also demonstrate an absolute increase of at least 5 mm. (Note: the appearance of one or more new lesions is also considered progressions).

Stable Disease (SD): Neither sufficient shrinkage to qualify for PR nor sufficient increase to qualify for PD, taking as reference the smallest sum diameters while on study.

12.1.4.2 Evaluation of Non-Target Lesions

Complete Response (CR): Disappearance of all non-target lesions and normalization of tumor marker level. All lymph nodes must be non-pathological in size (<10 mm short axis).

Note: If tumor markers are initially above the upper normal limit, they must normalize for a patient to be considered in complete clinical response.

Non-CR/Non-PD: Persistence of one or more non-target lesion(s) and/or maintenance of tumor marker level above the normal limits.

Progressive Disease (PD): Appearance of one or more new lesions and/or unequivocal progression of existing non-target lesions. Unequivocal progression should not normally trump target lesion status. It must be representative of overall disease status change, not a single lesion increase.

Although a clear progression of “non-target” lesions only is exceptional, the opinion of the treating physician should prevail in such circumstances, and the progression status should be confirmed at a later time by the review panel (or MSKCC Principal Investigator).

